3.1 Inclusion Criteria.....	18
3.2 Exclusion Criteria	18

PROTOCOL SYNOPSIS

TITLE	A Pilot Study of ^{68}Ga -RM2 PET/MRI in the Evaluation of Patients with Estrogen Receptor-positive Breast Cancer
STUDY PHASE	Pilot study
INDICATION	Breast cancer
INVESTIGATIONAL PRODUCTS	^{68}Ga -RM2; also known as: 
• Bombesin• BAY86-7548
SAMPLE SIZE	20 participants
PRIMARY OBJECTIVE	To evaluate the feasibility of ^{68}Ga -RM2 PET/MRI for identification of estrogen receptor positive primary breast cancer and metastases

SCHEMA

LIST OF ABBREVIATIONS AND DEFINITION OF TERMS

Ga-68; ^{68}Ga	Gallium-68
IRB	Institutional Review Board
IV	Intravenous
PET/MRI	Positron emission tomography – magnetic resonance imaging
SUV	Standardized Uptake Value
GRPr	Gastrin releasing peptide receptor
ER	Estrogen receptor

1. OBJECTIVE

Specific Aim

To evaluate the feasibility of ^{68}Ga -RM2 PET/MRI for identification of estrogen receptor positive primary breast cancer and metastases.

2. BACKGROUND

2.1 Preliminary information

Breast cancer is a leading cause of cancer-related death found in women worldwide, with a steadily increasing incidence in many countries over the past 30 years (1). Thus, early detection and thorough evaluation of primary breast cancer and its metastases may lead to a higher rate of successful treatment and extend the patient's life span. Currently, the diagnosis of breast cancer is usually determined using anatomical imaging, such as x-ray mammography, ultrasound, and MRI, and is confirmed via biopsy.

With the advent of molecular imaging, nuclear medicine techniques are considered to hold promise for the early detection of tumors through a functional perspective, providing information on molecular characteristics.

GRPR is known as a G-protein-coupled receptor that is expressed in a series of cancer types, including breast cancer, small cell lung cancer, prostate cancer, glioma, and neuroblastoma. According to literature, 62% to 96% of estrogen receptor positive (ER+) breast cancers express GRPR (2). Gastrin-releasing peptide receptor is heterogeneously expressed in neoplastic epithelial mammary cells, ductal carcinomas *in situ*, and invasive carcinoma. GRPR is also expressed in metastatic lymph nodes from breast cancer, whereas the level of GRPR expression in normal lymph node tissue is very low.

^{68}Ga -labeled DOTA-4-amino-1-carboxymethyl-piperidine-D-Phe-Gln-Trp-Ala-Val-Gly-His-Sta-Leu-NH₂ (^{68}Ga -DOTA-Bombesin or ^{68}Ga -RM2, formerly also known as BAY86-7548) is a synthetic bombesin receptor antagonist, which targets gastrin-releasing peptide receptors (GRPR) (3). Stoykow and colleagues reported the use of ^{68}Ga -RM2 in 15 patients with breast cancer. A total of 13 of 18 tumors demonstrated strongly increased ^{68}Ga -RM2 uptake compared to normal breast tissue (defined as PET-positive). All PET-positive primary tumors were ER- and PR-positive (13 of /13) in contrast to only 1 of 5 PET-negative tumors. Mean SUV_{max} of ER-positive tumors was 10.6 ± 6.0 compared to 2.3 ± 1.0 in ER-negative tumors ($P = 0.016$). In a multivariate analysis including ER, PR, HER2/neu and MIB-1, only ER expression predicted ^{68}Ga -RM2 uptake (model: $r^2 = 0.55$, $p = 0.025$). Normal breast tissue showed inter- and intraindividually variable, moderate GRPR binding (SUV_{max} 2.3 ± 1.0), while physiological uptake of other organs was considerably less except pancreas. Of note, ^{68}Ga -RM2-PET/CT detected internal mammary lymph nodes with high ^{68}Ga -RM2 uptake ($n = 8$), a contralateral axillary lymph node metastasis (verified by biopsy) and bone metastases ($n = 1$; not detected by bone scan and CT). This study demonstrated that ^{68}Ga -RM2-PET/CT is a promising imaging method in ER-positive breast cancer. *In vivo* GRPR binding assessed by ^{68}Ga -RM2-PET/CT correlated with ER expression in primary tumors of untreated patients (4).

We conducted a pilot phase evaluation of ^{68}Ga -RM2 in prostate cancer patients under an RDRC-approved protocol at Stanford University. Ten men (age range: 60 to 83 year-old; mean \pm SD: 73.1 ± 6.9) with biochemical recurrence of prostate cancer (PSA range: 3.7 to 36.4; mean \pm SD: 12.5 ± 9.8) were enrolled. PET/MRI images were acquired at

42 to 51 minutes (mean \pm SD: 47.2 ± 3.2) after injection of 3.6 to 4.1 mCi (mean \pm SD: 3.7 ± 0.2) of ^{68}Ga -RM2.

Biodistribution and localization of ^{68}Ga -RM2

All participants tolerated the procedure without immediate or delayed (up to 7 days) complaints or complications. Table 2 shows the ^{68}Ga -RM2 uptake (SUV_{max} and SUV_{mean}) in normal tissues. The areas with the highest ^{68}Ga -RM2 accumulation are the pancreas (mean SUV_{max}: 52.0 ± 16.7 [range: 36.8 to 93.8] and SUV_{mean}: 33.2 ± 17.5 [range: 8.8 to 66.1]) and bladder (mean SUV_{max}: 121.6 ± 67.5 [range: 32.6 to 220.7] and SUV_{mean}: 93.8 ± 59.7 [range: 29.8 to 195.7]), while moderate uptake was noted in the blood pool (mean SUV_{max}: 2.3 ± 0.7 [range: 1.8 to 4.0] and SUV_{mean}: 1.3 ± 0.7 [range: 0.7 to 2.7]), stomach (mean SUV_{max}: 2.5 ± 0.7 [range: 1.3 to 3.7] and SUV_{mean}: 1.3 ± 0.5 [range: 0.6 to 1.9]), small bowel (mean SUV_{max}: 2.4 ± 0.6 [range: 1.7 to 3.3] and SUV_{mean}: 1.4 ± 0.5 [range: 0.7 to 2.3]) and colon (mean SUV_{max}: 2.0 ± 0.7 [range: 1.3 to 3.8] and SUV_{mean}: 1.0 ± 0.6 [range: 0.5 to 2.3]). The liver had low ^{68}Ga -RM2 uptake with SUV_{mean} of less than 1.0. There were no differences between the ^{68}Ga -RM2 biodistribution at 45 minutes post-injection among the 10 participants (Figure 1). The pattern of ^{68}Ga -RM2 uptake is similar to previous reports (5).

[figure not shown]

Figure 1: Maximum intensity projection (MIP) images from 10 participants in the prostate cancer pilot study conducted at Stanford University.

The sponsor-investigator [name] holds an Investigational New Drug application (IND) for ^{68}Ga -RM2 (IND 127137), and the group has significant experience using the tracer in currently ongoing clinical studies in prostate cancer at our institution, including 81 patients with biochemically recurrent prostate cancer and 16 patients with newly diagnosed prostate cancer. We propose to extend the use in patients with estrogen receptor positive (ER+) breast cancer.

2.2 Clinicaltrials.gov

This protocol will be registered on Clinicaltrials.Gov. ClinicalTrials.gov outcomes are described at Section 2.4.3.

2.3 Rationale

In this study, we propose to use a well-established PET isotope, Gallium-68 (^{68}Ga), bound to a bombesin receptor antagonist, ^{68}Ga -RM2, which has high affinity for gastrin-releasing peptide receptors. GRPR proteins are highly overexpressed in several human tumors, including breast cancer (2). The following aim is proposed:

To evaluate the feasibility of ^{68}Ga -RM2 PET/MRI for identification of ER+ primary breast cancer and metastases.

The first-in-human study investigated the safety, tolerability, metabolism, pharmacokinetics, biodistribution, and radiation dosimetry of ^{68}Ga -RM2. Five healthy men underwent dynamic whole-body PET/CT after an intravenous injection of ^{68}Ga -RM2 ($138 \pm 5 \text{ mBq}$). Besides total radioactivity, plasma samples were analyzed by radio-high-performance liquid chromatography for metabolism of the tracer. Dosimetry was calculated using the OLINDA/EXM software. The organs with the highest absorbed doses were the urinary bladder wall (0.62 mSv/MBq) and the pancreas (0.51 mSv/MBq). The mean effective dose was 0.051 mSv/MBq. ^{68}Ga -RM2 was well tolerated by all subjects. The authors concluded that the intravenously injected ^{68}Ga -RM2 is safe, and rapid metabolism is demonstrated. A 150-MBq injection of ^{68}Ga -RM2 results in an effective dose of 7.7 mSv, which could be reduced to 5.7 mSv with frequent bladder voids (5).

[figure not shown]

Figure 2: 74-year-old patient with a bilateral tumor with an ER/PR-positive tumor on the right side (PET-positive) and an ER/PR-negative tumor on the left side (PET-negative). Maximum intensity projection (left); CT (upper row); ^{68}Ga -RM2-PET (lower row); primary tumors indicated by red arrows (4).

2.4 Study Design

This is a pilot study enrolling up to 20 participants with ER+ breast cancer, either at initial diagnosis prior to surgery or at suspected recurrence. Eligible participants will undergo baseline assessments at enrollment. Study participants will receive ^{68}Ga -RM2 and undergo a PET/MRI scan. All patients will first be seen by a Stanford Cancer Institute physician and then referred if appropriate on clinical grounds to [name] or his colleagues for this study. The following steps will take place.

1. Participants will be given a copy of the consent form s/he signed.
2. Participant will be asked to drink 1 to 2 glasses of water before arrival at the clinic
3. Vital signs (heart rate, blood pressure) will be recorded
4. Participant will be injected IV with $140 \pm 20\%$ mBq of ^{68}Ga -RM2
5. Participant will void immediately prior to the scan
6. Data acquisition will begin with a dedicated scan of the breasts, followed by a vertex to mid-thighs scan. First, localizer MRI scans will be performed to define the table positions and then MR structural imaging and diffusion weighted imaging will be performed simultaneously with PET imaging. After the dedicated scan of the breasts, a whole-body combined PET/MRI acquisition will be initiated with 3 to 5 table positions at a 2 to 4 minute acquisition time per table position.
7. Vital signs (heart rate, blood pressure) will be recorded again at the completion of the study, and the patient will be dismissed.
8. Participants will be contacted at 24 to 72 hours following the scan in order to collect record any adverse events.

2.4.1 Objectives of the Study

Primary Objective

- To evaluate the feasibility ^{68}Ga -RM2 PET/MRI for identification of estrogen receptor positive primary breast cancer and metastases

2.4.2 Endpoints

Primary Endpoints

- Number of lesions identified on ^{68}Ga -RM2 PET/MRI
- Correlation of ^{68}Ga -RM2 uptake and ER positivity on biopsy (when done as clinically indicated)

2.4.3 ClinicalTrials.gov Outcomes

Primary Outcome

Title: Number of lesions identified on ^{68}Ga -RM2 PET/MRI

Description: Findings deemed as compatible with breast cancer

The outcome will be reported as the number of participants with successful PET-based detection of ER-positive breast cancer and metastases

Timeframe: 12 months

Safety outcome: No

Secondary Outcome

None

3. PARTICIPANT SELECTION AND ENROLLMENT PROCEDURES

3.1 Inclusion Criteria

1. ≥ 18 years-old
2. Biopsy proven ER+ breast cancer, either at initial diagnosis prior to surgery or at suspected recurrence.
3. Able to provide written consent
4. Karnofsky performance status of ≥ 50 (or ECOG/WHO equivalent)
5. Females must be not be pregnant per urine pregnancy test

3.2 Exclusion Criteria

1. Inability to lie still for the entire imaging time Inability to lie still for the entire imaging time
2. Inability to complete the needed investigational and standard-of-care imaging examinations due to other reasons (severe claustrophobia, radiation phobia, etc.)
3. Any additional medical condition, serious intercurrent illness, or other extenuating circumstance that, in the opinion of the Investigator, may significantly interfere with study compliance
4. Metallic implants (contraindicated for MRI)

3.3 Informed Consent Process

All participants will be provided a consent form describing the study with sufficient information for participants to make an informed decision regarding their participation. Participants must sign the IRB approved informed consent prior to participation in any study specific procedure. The participant must receive a copy of the signed and dated consent document. The original signed copy of the consent document must be retained in the medical record or research file.

3.4 Study Timeline

3.4.1 Primary Completion:

The study will reach primary completion 24 months from the time the study opens to accrual.

[figure not shown]
3.4.2. Study Completion:

The study will reach study completion 36 months from the time the study opens to accrual.

4. IMAGING AGENT INFORMATION

4.1 Study Agent ^{68}Ga -RM2

The PET radiopharmaceutical ^{68}Ga -RM2 has previously been identified as ^{68}Ga -DOTA Bombesin or BAY86-7548. This is not an FDA-approved product, and is described within IND 127137, the IND to which this protocol is submitted. The structure of ^{68}Ga -RM2 is represented in Figure 3.

BAY 86-7548

Figure 3: Chemical structure of ^{68}Ga -RM2

The administered dosage of ^{68}Ga -RM2 will be $140 \text{ mBq} \pm 20\%$, administered IV. The administered dosage is 140 mBq i.v. Measured human dosimetry data are available from published data (5). ^{68}Ga -RM2 is rapidly excreted through the kidneys to the urinary bladder and accumulated predominantly in the pancreas and liver. Maximum peak uptake of the total injected radioactivity was seen in the urinary bladder contents and the liver, with approximately 36% and 14%, respectively.

The organ with the highest absorbed dose was the urinary bladder wall at 0.61 mSv/MBq , followed by the pancreas at 0.51 mSv/MBq . The mean effective dose (14) was 0.051 mSv/MBq . Thus, the effective dose from a 140 MBq injected radioactivity is 7.7 mSv , which could be reduced to roughly 4.76 mSv with frequent bladder voiding (1-h voids).

To summarize the results of the published human dosimetry study, there were no observed adverse events to the radiopharmaceutical. The measured dosimetry showed that the critical organ with ^{68}Ga -RM2 is the urinary bladder, followed by the pancreas. The effective dose of ^{68}Ga -RM2 reported (0.051 mSv/MBq) is approximately twice as much as those of ^{68}Ga -DOTA-TOC (0.023 mSv/MBq), ^{68}Ga -DOTA-NOC (0.025 mSv/MBq), ^{68}Ga -DOTA-TATE (0.021 mSv/MBq) and ^{68}Ga -NOTA-RGD (0.022 mSv/MBq) (6-9).

4.3 Ordering

Ordered in Radiology Information System (RIS), address per above.

4.4 Agent Accountability

The RIS is password-protected and part of the electronic medical records.

5. IMAGING SPECIFICS

5.1 Modality or Modalities to be used

PET/MRI

5.2 Details of Imaging (ie, dynamic, static, number of scans, etc)

First a standard breast MRI will be done, at the discretion of the investigator. After correct positioning of the spatial acquisition windows is ensured, the combined PET/MRI acquisition will be initiated with 3 to 5 table positions at a 2 to 4 min acquisition time per table position. A volumetric T1 acquisition with fat-water separation and motion correction to enable free-breathing will be obtained at each table position and used for the generation of attenuation maps and for anatomic allocation of the PET results. Simultaneously with the start of the T1 MRI sequence, the PET acquisition will start at the same table position, thus ensuring optimal temporal and regional correspondence between MRI and PET data. The PET acquisition time will be 4 min per table position, taking delayed acquisition times and radioactive decay into account. As the T1 will take less than 4 minutes, a rapid diffusion weighted MRI will also be performed. After completion of the PET acquisition, the table will be moved to the next table position and the procedure will be repeated. Upon completion of the PET acquisition for all stations, volumetric T1- and T2-weighted MR images may be obtained at multiple stations as needed.

The PET emission scan is corrected using segmented attenuation data of the MRI scan. The PET images are reconstructed with a standard iterative algorithm. All images are reformatted into axial, coronal, and sagittal views and viewed with the software provided by the manufacturer (AW, GE Medical Systems).

5.3 Image interpretation

The PET/MRI scans will be interpreted by ABNM certified Nuclear Medicine physicians and ABR certified Radiologists. Drs [name], [name], [name] and [name] have significant clinical experience and will be blinded to the participants' medical history and the results of other imaging modalities. Consensus read will be obtained for each scan. Each lesion will be tabulated and a comparison of lesion detection by each scanner will be conducted.

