10.1 Study Endpoints

Primary endpoint:

- Number of participants with successful PET-based detection of ER-positive breast cancer and metastases

Other endpoints:

None

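### PET sensitivity is to be scored from a joint read of PET and MRI, with no PET-first step and no uptake criterion, so it can be biased upward

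*Combined protocol and SAP*

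**What the plan says.** Section 10.1 gives the primary endpoint as "Number of participants with successful PET-based detection of ER-positive breast cancer and metastases". Section 10.3 says that the only estimate will be per-lesion sensitivity of PET-based detection of known ER+ lesions. It expects at least 80% and calls 75% the minimum that would justify further study.

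Section 5.3 describes the read: "The PET/MRI scans will be interpreted by ABNM certified Nuclear Medicine physicians and ABR certified Radiologists". The readers "will be blinded to the participants' medical history and the results of other imaging modalities". Then: "Consensus read will be obtained for each scan", and "Each lesion will be tabulated and a comparison of lesion detection by each scanner will be conducted".

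Section 5.2 describes what the examination contains. The T1 series is "used for the generation of attenuation maps and for anatomic allocation of the PET results", and a rapid diffusion-weighted series is acquired alongside PET. It also says: "First a standard breast MRI will be done, at the discretion of the investigator". Whether the readers in 5.3 see that breast MRI is not stated.

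Section 2.4.2 states a different primary endpoint, the number of lesions identified on the PET/MRI as a whole. Section 2.4.3 carries that title, asks for findings judged compatible with breast cancer, and then reports participants with PET-based detection.

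**The concern.** The quantity estimated belongs to PET, but the read that supplies it belongs to PET and MRI together. The blinding covers medical history and other modalities; it is not said to cover the MRI from the same session. All participants have biopsy-proven ER+ disease (Section 3.1), and the analysis is of sensitivity alone, so a generous call carries no penalty in specificity. Where uptake is doubtful and the MRI is clear, nothing in the plan stops the lesion being recorded as PET-detected.

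At stake is whether the pilot's main number describes the tracer or the combined examination. The number is meant to inform whether the tracer deserves further study, and any error of this kind favours the tracer.

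**Working it through.** **Step 1. Set the sections side by side.**

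- Estimated: PET-based detection (10.1) and PET sensitivity (10.3).
- Read: the combined PET/MRI, by consensus (5.3).
- Reading order, or a PET list fixed before MRI is viewed: none in 5.2, 5.3 or 10.
- Criterion for a PET-positive lesion: none. Section 2.4.3 relies on reader judgement. Section 2.1 cites a 15-patient breast cancer study of the same tracer that defined PET-positive as strongly increased uptake compared with normal breast, but the protocol does not adopt that definition.

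**Step 2. Reproduce the plan's own figure.** Section 10.3 claims 90% power at one-sided 5% with n = 20 and sensitivity 80%, against chance. No number is given for chance; I assume 50%. By the normal approximation:

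power = Φ[(0.80 − 0.50 − 1.645 × √(0.25/20)) / √(0.16/20)] = Φ[(0.300 − 0.184)/0.0894] = Φ(1.30) = 0.903.

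The 90% reproduces. With the exact binomial, the smallest count that keeps one-sided error within 5% is 15 of 20 (error 0.021, power 0.804); 14 of 20 has error 0.058. Scoring PET separately changes neither n nor this nominal power. What is in doubt is the sensitivity fed into it.

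**Step 3. Effect of MRI credit.** Let s be the true PET sensitivity and f the share of PET-missed known lesions credited through MRI. Then

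apparent sensitivity = s + (1 − s) × f.

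The documents do not give f, so a range is shown. For s I use the plan's expected 80%, the assumed chance level of 50%, and 60% as a case below the plan's 75% minimum. The second figure in each cell is the binomial probability of at least 15 of 20, treating the 20 lesions as independent.

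| True s | f = 0 | f = 10% | f = 25% | f = 50% |
|---|---|---|---|---|
| 50% | 50%; 0.021 | 55%; 0.055 | 62.5%; 0.179 | 75%; 0.617 |
| 60% | 60%; 0.126 | 64%; 0.217 | 70%; 0.416 | 80%; 0.804 |
| 80% | 80%; 0.804 | 82%; 0.864 | 85%; 0.933 | 90%; 0.989 |

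In lesions: at s = 60%, PET misses 8 of 20, and crediting half of them turns 12 detections into 16. At s = 80%, it misses 4, and crediting half turns 16 into 18.

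The 15-of-20 mark is a benchmark of mine. It is the exact critical count from Step 2 and equals 75%, but the protocol states no such rule and attaches its 75% to a sample of 25.

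**The case against.** Four points can be made for the plan.

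- **The endpoint already says PET-based.** A lesion seen only on MRI does not meet it as worded, and readers who apply the wording strictly produce no bias. This stands as a limit: a reader might infer that the estimate is certainly biased, and the documents do not show that. It does not close the gap, because Section 5.3 gives the readers no procedure or criterion for applying the wording.
- **The objective concerns PET/MRI.** Sections 1 and 2.4.1, and the lesion count in 2.4.2, evaluate the combined examination, for which a joint read is the right read and MRI's contribution is not bias. This stands. The point is confined to 10.1, 10.3 and the reporting line of 2.4.3.
- **The plan promises "a comparison of lesion detection by each scanner will be conducted".** A reader might infer that this is impossible because the study has one PET/MRI examination. That goes too far. Sections 3.2 and 6.3 refer to standard-of-care imaging, so the phrase could mean PET/MRI against that imaging, or PET against MRI. It is undefined, and it is not tied to the PET-based endpoint.
- **Uptake is measured anyway.** Section 2.4.2 also lists the correlation of uptake with ER positivity on biopsy, so it would be too strong to say that the study cannot isolate the tracer at all. But that endpoint covers only lesions biopsied for clinical reasons, is absent from 10.1, and does not define a detected lesion.

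It is also fair that 5.3 does not rule out independent reads before the consensus. These would not help unless they were made on PET without the diagnostic MRI.

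**Conclusion.** The concern holds as a risk with a known direction and an unknown size. Following Section 5.3 as written can give a PET sensitivity that is too high, because known lesions can be credited from MRI and nothing in the analysis offsets that. For f between 10% and 50%, the inflation is 4 to 20 percentage points at a true sensitivity of 60%, and 2 to 10 points at the expected 80%. At f = 0 it is nil. The true sensitivities other than 80%, and every value of f, are assumptions. The credit model further assumes that MRI affects only PET-missed lesions and never removes a PET call. Moderate credit could carry a tracer that falls short of the plan's 75% minimum past it. For a 20-participant pilot this is a correction that should be made before the scans are read; it does not invalidate the design.

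**What to change.** In Section 5.3:

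- Have the same readers score each lesion on PET first, with MR used only for attenuation correction and anatomic allocation. Lock those calls before the diagnostic breast MRI and diffusion images are opened.
- State a PET-positivity criterion in advance, for example uptake increased relative to normal breast tissue, as in the study cited in Section 2.1. Name the reference tissue for lesions outside the breast. Without a criterion, a locked read is still a matter of impression.
- Define what each scanner means, for example locked PET against combined PET/MRI, or PET/MRI against standard-of-care imaging. A PET read followed by a combined read does not yield an MRI-alone result; if PET against MRI is wanted, a separate MRI read must be added.

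In Sections 10.1 and 10.3, and the reporting line of 2.4.3, say that only the locked PET calls count. Report the combined read separately for the Section 2.4.2 lesion count.

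The cost is a few more reading minutes per scan and one more data column for 20 scans, with no new readers, scans or patient procedures. The PET sensitivity may come out lower. Some anatomical cue remains through the localising MR, so the risk is reduced and not removed. The change must precede reading, because an uncontaminated PET score is hard to recover afterwards.
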